2.2 Secondary endpoints

- a. Proportion of patients with positive margins after standard of care breast-conserving surgery who have a LUM Imaging System signal in the cavity above the threshold as defined by the tumor detection algorithm (i.e., a positive LUM signal).
- b. Proportion of subjects with pathology-positive margins after standard of care breast-conserving surgery for whom additional LUM Imaging System-guided shaves resulted in pathology-negative margins among patients with positive margins. Note: This endpoint also estimates the potential reduction in re-excision surgeries following standard of care breast-conserving surgery that resulted from a positive SOC margin.
- c. Proportion of subjects with pathology-positive margins after standard of care breast-conserving surgery for whom additional LUM Imaging System-guided shaves resulted in pathology-negative margins among all patients.
- d. Ratio of patients with negative margins after the SOC procedure who have residual cancer found in at least one Lumicell-guided (or therapeutic) shave among patients with negative margins.
- e. Ratio of patients with negative margins after the SOC procedure who have residual cancer found in at least one Lumicell-guided (or therapeutic) shave among all patients
- f. Mean and median incremental volume (in cubic centimeters) of tissue removed from therapeutic shaves: For each patient, absolute shave volume will be calculated as length (c) × width (c) × depth (c) for each therapeutic shave with the sum by patient of all therapeutic shaves. Subjects with no therapeutic shaves taken will have a therapeutic shave volume of 0cc.
- g. Mean and median contribution of therapeutic shave volume to total tissue removed.
- h. Comparison of adverse events in subjects that have at least one therapeutic shave versus subjects that have no therapeutic shaves.

- i. Average number of therapeutic shaves taken per subject overall and by type of SOC lumpectomy procedure (i.e., lumpectomy with comprehensive shaves vs. lumpectomy with or without selective shaves).
- j. Percent of device failures that led to failure of using the LUM Imaging System to capture data.
- k. Rate of re-excision procedures as a result of a positive margin status following SOC (control arm) and LUM Imaging procedures (device arm).
- l. Number of re-excisions for each patient
- m. Number of re-excisions recommended
- n. Collect exploratory data on tissue types found in therapeutic shaves.

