3.3 Secondary endpoints

- a. Proportion of patients with positive margins after standard of care breast-conserving surgery who have a LUM Imaging System signal in the cavity above the threshold as defined by the tumor detection algorithm (i.e., a positive LUM signal). The endpoint is mathematically defined as:

$$\frac{\# \text{ positive margin patients after SOC with LUM signal above the threshold}}{\# \text{ positive margin patients after SOC}}$$

If a subject has more than one orientation with an SOC positive margin, LUM imaging must correctly identify all orientations with an SOC positive margin for success of this endpoint.

- b. Proportion of subjects with pathology-positive margins after standard of care breast-conserving surgery for whom additional LUM Imaging System-guided shaves resulted in pathology-negative margins. Note: This endpoint also estimates the potential reduction in re-excision surgeries following standard of care breast-conserving surgery that resulted from a positive SOC margin. This is estimated as:

$$\frac{\# \text{ positive margin patients after SOC with all final negative margins after the LUM procedure}}{\# \text{ positive margin patients after SOC}}$$

- c. Proportion of subjects with pathology-positive margins after standard of care breast-conserving surgery for whom additional LUM Imaging System-guided shaves resulted in pathology-negative margins among all patients. This is estimated as:

$$\frac{\# \text{ positive margin patients after SOC with all final negative margins after the LUM procedure}}{\text{Total number patients}}$$

- d. Ratio of patients with negative margins after the SOC procedure who have residual cancer found in at least one Lumicell-guided (or therapeutic) shave among patients with negative margins. This is estimated as:

$$\frac{\# \text{ negative margin patients after SOC with residual cancer found in at least one therapeutic shave}}{\# \text{ negative margin patients after SOC}}$$

- e. Ratio of patients with negative margins after the SOC procedure who have residual cancer found in at least one Lumicell-guided (or therapeutic) shave among all patients

$$\frac{\# \text{ negative margin patients after SOC with residual cancer found in at least one therapeutic shave}}{\text{Total number of patients}}$$

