4.3.2 Performance goals

The verification of the sensitivity and specificity co-primary endpoints will be a refutation of the null hypotheses

$$H_{01}^s: sen \leq 40\% \text{ against the alternative } H_{11}^s: sen > 40\%$$

$$H_{02}^s: spec \leq 60\% \text{ against the alternative } H_{12}^s: spec > 60\%$$

where *sen* and *spec* represent the true sensitivity and specificity, respectively. The hypotheses involving sensitivity and specificity will be assessed based on the data collected per-tissue level.

These hypotheses will be tested using a one-sided significance level of 2.5%. To account for within-subject correlation, Generalized Estimating Equations (GEE), with a compound symmetry working correlation structure, will be used to estimate sensitivity and specificity along with an equi-tail 95% two-sided confidence interval (CI). The null hypothesis H_{01}^s is rejected if the lower bound of the confidence interval for sensitivity is larger than the performance goal of 40%. Similarly, the null hypothesis H_{02}^s is rejected if the lower bound of the confidence interval for specificity is larger than the performance goal of 60%.

Performance Goals selection for sensitivity and specificity endpoints

Data from the Phase C Feasibility Study showed pathology margin assessment sensitivity to predict cancer in the cavity of ~40%. However, this pathology assessment is done several days after the surgery and can lead to second surgeries. Because the LUM Imaging System provides the additional benefit of assessing the cavity in real-time, a performance goal for instrument sensitivity > 40% is proposed as the success criterion for this hypothesis-tested endpoint. We expect the sensitivity to be similar to that observed in the Phase C study of 69% [95% CI: 56%-80%].

LUMICELL CONFIDENTIAL

This document is confidential. Do not disclose or use except as authorized.

The Phase C data shows that at the current specificity performance of 70% [95% CI: 68%-73%], an average of 1.1 additional shaves were removed guided by the LUM Imaging system, accounting for ~10% of all the total resected tissue. We selected a performance goal for specificity of > 60% to ensure that similar performance in the pivotal trial is obtained regarding tissue removal. Also, with this lower bound, a Youden Index > 0 will be demonstrated to indicate non-random diagnostic performance.

Sample size for testing sensitivity:

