As sensitivity and specificity are estimated at the per tissue level, within subject correlation is considered for the sample size estimation. Intraclass Correlation Coefficient (ICC) was estimated with data from the Feasibility Phase C study. The ICC value was obtained at 0.145 for the full phase data set and at 0.22 for the validation data set which the tumor detection algorithm is same as that used in the pivotal study. We selected ICC at 0.22 for sample size estimation.

The parameters for the simulation is as below:

- True sensitivity is 60%
- Intraclass Correlation Coefficient (ICC) value = 0.22
- Truth standard positive rate 4%
- Performance Goal (PG) = 40%
- 2.5% one-sided significance level
- 70 truth standard positive shaves

Assuming 70 truth standard positive shaves, under the alternative hypothesis, using Generalized Estimating Equation (GEE) model with a compound symmetry working correlation structure, will have >90% power to show that the true sensitivity is > 40%.

Sample size for testing specificity:

The parameters for the simulation is as below:

- True specificity is 65%
- Intraclass Correlation Coefficient (ICC) value = 0.22
- Truth standard negative rate 96%
- Performance Goal (PG) = 60%
- 2.5% one-sided significance level

Under the alternative hypothesis, using Generalized Estimating Equation (GEE) model with a compound symmetry working correlation structure, 1023 truth standard negatives are needed to reach >90% power to show that the true specificity is >60%.

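### Secondary endpoint a states an orientation match only for patients with several SOC-positive orientations; read literally, a missed single positive margin counts as detected if any other wall signals

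*SAP*

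**What the plan says.** Protocol 2.2 a, repeated in 15.4.3 a, takes patients with positive margins after SOC and counts those "who have a LUM Imaging System signal in the cavity above the threshold as defined by the tumor detection algorithm". It does not say where in the cavity the signal must be.

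SAP 3.3 a keeps that wording and adds a formula whose numerator is "positive margin patients after SOC with LUM signal above the threshold". The formula names no orientation either. One sentence follows it, and it is conditional: "If a subject has more than one orientation with an SOC positive margin, LUM imaging must correctly identify all orientations" that have such a margin.

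Nothing is said about a patient with exactly one SOC-positive orientation. SAP 4.7 (additional analyses), 4.11.2 (several images or shaves) and 4.11.3 (missing and spurious data) add no matching rule for this endpoint. SAP 4.4 separately defines a per-patient analysis in which one positive signal anywhere makes the patient positive.

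**The concern.** The device is meant to show the surgeon where to cut. A signal on one wall does not direct a shave to a positive margin on another. Under the literal wording, a patient with one positive orientation succeeds if any imaged wall signals, while a patient with two succeeds only if both are flagged. The pooled proportion then depends on the mix of the two kinds of patient as well as on the device.

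Endpoint a is listed first among the secondary endpoints and resembles the feasibility result in Protocol 3.2 (9 of 11 subjects with positive margins, 82%), so it is likely to be read as a detection rate. It has no specificity reported with it that would show how much of the rate comes from signals elsewhere. A programmer following the SAP formula would have no instruction to match the orientation when only one is positive.

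**Working it through.** The plan gives no target, power or sample size for endpoint a, so there is no figure of its own to reproduce. The check sizes the gap between the two readings for a patient with exactly one SOC-positive orientation.

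**Inputs from the documents**
- Detection at the positive orientation, s: 67% (Phase C per-tissue sensitivity, Protocol 15.3.2). SAP 4.3.2 gives 69%; the power assumption is 60%.
- Orientations: up to six (SAP 4.4), so up to five others. Walls without removable tissue are not imaged (Protocol 5.2.8.1, 5.3.1).
- Phase C specificity 70% (SAP 4.3.2), so 30% of truth-negative tissues signal.
- Phase C average of 1.1 guided shaves per patient (SAP 4.3.2).
- ICC 0.22 (SAP 4.3.2, sample size for sensitivity).

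**Assumptions not in the documents**
- Three to five other walls are imaged.
- The lower per-wall signal rate is 1.1/6 = 18%. This treats shaves as a proxy for positive walls, although not every signal yields a shave.
- Detection at the positive wall is independent of signals elsewhere.
- Per-tissue sensitivity against the hierarchical truth standard stands in for detection at an SOC-positive margin.

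**Formulas.** Let f be the per-wall signal rate and k the number of other walls.
- Independent walls: P(any other signal) = 1 − (1 − f)^k.
- Correlated walls: beta-binomial with mean f and the stated ICC. With c = (1 − ICC)/ICC, a = fc and b = (1 − f)c, P(no signal) is the product of (b + j)/(a + b + j) for j = 0 to k − 1.
- Any-signal success = s + (1 − s) × P(any other signal). Matched success = s.

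**Results at s = 67%**

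| f | k | Correlation | P(any other signal) | Any-signal success |
|---|---|---|---|---|
| 30% | 5 | none | 83% | 94% |
| 30% | 5 | ICC 0.22 | 69% | 90% |
| 30% | 3 | none | 66% | 89% |
| 30% | 3 | ICC 0.22 | 57% | 86% |
| 18% | 5 | none | 64% | 88% |
| 18% | 5 | ICC 0.22 | 49% | 83% |
| 18% | 3 | none | 46% | 82% |
| 18% | 3 | ICC 0.22 | 38% | 80% |

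For example, the first row is 1 − 0.7^5 = 0.832, and 0.67 + 0.33 × 0.832 = 0.94. The matched rule gives 67% in every row.

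**Correlation with the missed wall.** If the missed wall shares the ICC of 0.22 with the others, P(any other signal) becomes 1 − P(none in k + 1)/(1 − f). At f = 30% and k = 5 this is 1 − 0.273/0.70 = 61%, and success is 87% instead of 90%. In the last row it is 32%, and success is 78% instead of 80%.

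**The strict rule for comparison.** With two positive orientations and s = 67%, both are flagged with probability 0.67² = 45% if independent, or 0.449 + 0.22 × 0.67 × 0.33 = 50% with ICC 0.22.

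**The case against.** The strongest reply is that matching was always meant. The SAP says that LUM "LUM imaging must correctly identify all orientations with an SOC positive margin for success of this endpoint". It would be odd to demand location at two margins and none at one, so the sentence may only settle any-versus-all when there are several. That is a plausible account of intent, and it stands to this extent: the wording is a gap and does not show a deliberate choice. But the sentence is conditional, the formula names no orientation, and no other section extends the rule.

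A second reply is that the protocol leaves the full analysis to the SAP (Protocol 15), so the SAP elaborates the endpoint and does not contradict it. That is fair as to form, but under the protocol wording alone no patient needs a match.

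Third, other analyses limit the damage. Co-primary sensitivity and specificity are per tissue and score a missed orientation as a miss. SAP 4.4 pairs the any-signal measure with specificity. Endpoint b requires all final margins to be negative. Endpoint a has no hypothesis test. All of this stands and keeps the severity down.

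Fourth, a signal elsewhere need not be false. Margin pathology had only about 40% sensitivity for cancer in the cavity in Phase C (SAP 4.3.2), so such a signal may mark true residual cancer. This stands too, although that signal still does not detect the positive margin.

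A reader might infer that endpoint a as a whole will read 90% to 94%, or that most patients light up somewhere regardless of disease. The documents do not support either. Those figures are the upper end and apply to single-orientation patients only. The average of 1.1 guided shaves per patient, true positives included, also sits uneasily with a 30% signal rate over five other walls, which implies 5 × 0.30 = 1.5 false signals.

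**Conclusion.** The point holds as a defect of definition. Read literally, the success rule is lenient for one positive orientation and strict for several, and the protocol lacks the strict part. For single-orientation patients, the any-signal rule would report about 80% to 94% where the matched rule gives 67%, an excess of about 13 to 27 percentage points. This rests on the assumptions listed in the working; if the missed wall shares the correlation, the low end is about 78%. The share of positive-margin patients with one positive orientation is not given, so the effect on the overall endpoint cannot be stated. The co-primary endpoints are not affected. Severity is low to moderate.

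**What to change.** In Protocol 2.2 a and 15.4.3 a and in SAP 3.3 a, define success for every patient as a LUM-positive result in each orientation with an SOC positive margin, whether one or several, and make the SAP formula say the same. The any-signal patient-level measure stays in SAP 4.4.

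The SAP already refers to 406 enrolled patients (1.1), so the clarification should be dated before the analysis. If that is no longer possible, report both versions and label them.

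The cost is one sentence in each place. No new data are needed, because images are saved by orientation (Protocol 5.2.8.2) and combined into one result per orientation (SAP 4.11.2). The downside for the sponsor is a lower reported proportion.

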1 PURPOSE

The objective of this prospective, multi-center, two-arm randomized, blinded study is to demonstrate the safety and efficacy of the LUM Imaging System (LUM015 imaging agent in conjunction with the LUM Imaging Device and decision software), in identifying residual cancer in the lumpectomy bed of female breast cancer patients. The size of this study is driven by the necessary number of truth standard positive events; therefore, we propose an event-driven clinical study. Patients will be enrolled until 70 truth standard positive events are reported, up to a maximum of 450 patients.

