3.2 Rationale

Achieving negative margins during tumor excision is critical to assure that all or most of the cancer has been removed from the patient. Current standard of care dictates that tissue removed during surgery is analyzed post-operatively for tumor histology and margin assessment by a pathologist as described above. This procedure is time consuming, often requiring 7-10 days of pathology testing after the operation before margin status is known. In addition, this process is prone to sampling errors, as only a finite number of tissue slices can be examined, meaning that only a small fraction of the lumpectomy margin surface is assessed, < 1% of lumpectomy surface area by some estimates [2]. Thus, a safe method to directly assess the entire tumor bed intraoperatively and identify residual microscopic disease for immediate resection intraoperatively would be highly beneficial for patients.

Lumicell has developed the LUM Imaging System, which consists of a fluorescence-based imaging agent (LUM015), a hand-held, wide-field detector (LUM Imaging Device) that can image the lumpectomy cavity in seconds, and a tumor detection algorithm that highlights regions suspected to contain cancer and displays them on a computer monitor. The LUM Imaging system is intended to be used to scan the lumpectomy cavity walls intraoperatively after the resection of the main lumpectomy specimen.

The purpose of the Lumicell Imaging System is to enable surgeons to achieve negative margins during the initial surgery and eliminate or reduce the need for re-excision surgeries when compared with current standard of care procedures. Lumicell's system images the entire lumpectomy cavity surface in vivo, overcoming tissue handling and sampling limitations of standard pathology analysis of resected tissue. The LUM Imaging System provides real-time feedback to the surgeon about the status of the lumpectomy cavity walls.

The LUM Imaging System has been tested in a two-phase Feasibility Study at the Massachusetts General Hospital. There were 15 patients in Phase A and 45 patients in Phase B in the study. Of the 11 Lumicell imaged subjects for whom a pathology positive margin followed SOC, the LUM Imaging Device detected 9 (82%) of the subjects with residual cancer in the cavity. A multi-site Feasibility Phase C study is being conducted to refine and verify the tumor detection algorithm and to complete hands on training of surgeons and clinical staff.

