**STATISTICAL ANALYSIS PLAN FOR LUMICELL PROTOCOL NUMBER
CL0007r08**

Version Date: 17NOV2021

**Study Title: PIVOTAL STUDY OF THE LUM IMAGING SYSTEM FOR ASSISTING
INTRAOPERATIVE DETECTION OF RESIDUAL CANCER IN THE TUMOR BED OF
FEMALE PATIENTS WITH BREAST CANCER**

**System: LUM Imaging System (LUM015 imaging agent and LUM Imaging Device)
IDE # G140195**

[name].
[contact]
[contact]

[name]
[contact]

[name]
Statistical Consultant
[contact]

LUMICELL CONFIDENTIAL

This document is confidential. Do not disclose or use except as authorized.

TABLE OF CONTENTS

1	Introduction	2
1.1	Considerations for combining multiple datasets for safety analysis	2
2	Analysis Populations	2
3	Study endpoints	2
3.1	Definition of positive margins	2
3.2	Three co-primary endpoints	3
3.3	Secondary endpoints	6
4	Statistical methods	7
4.1	Demographics and baseline characteristics	7
4.2	Residual cancer removal	7
4.3	Sensitivity and specificity	8
4.4	Study sample size, event-driven design, and overall study power	11
4.5	Overall primary hypotheses	12
4.6	Methods for additional analyses	12
4.7	Safety analysis	12
4.8	Reported device issues	13
4.9	Protocol Deviations	14
4.10	General considerations	14
4.11	Analysis by additional diagnostic subgroups of interest	16
4.12	Exploratory Data Analyses	16
5	References	16

LUMICELL CONFIDENTIAL

This document is confidential. Do not disclose or use except as authorized.

1 Introduction

This document describes the statistical analysis plan to be performed as part of the pivotal study of the Lumicell Imaging System under protocol number CL0007r08. The objective of this prospective, multi-center, single-arm study is to demonstrate the safety and efficacy of the LUM Imaging System (LUM015 imaging agent in conjunction with the LUM Imaging Device and decision software), in identifying residual cancer in the lumpectomy bed of female breast cancer patients. For safety assessment, we propose two analyses: one analysis that pools all the patients that have received administration of LUM015 across all the clinical trial protocols including non-breast cancer indication, and another analysis for just breast cancer patients.

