- f. Mean and median incremental volume (in cubic centimeters) of tissue removed from therapeutic shaves: For each patient, absolute shave volume will be calculated as length (c) × width (c) × depth (c) for each therapeutic shave with the sum by patient of all therapeutic shaves. Subjects with no therapeutic shaves taken will have a therapeutic shave volume of 0cc.

- g. Mean and median contribution of therapeutic shave volume to total tissue removed.

LUMICELL CONFIDENTIAL

This document is confidential. Do not disclose or use except as authorized.

- h. Average number of SOC and therapeutic shaves taken per subject overall and by type of SOC lumpectomy procedure (i.e., lumpectomy with comprehensive shaves vs. lumpectomy with or without selective shaves).
- i. Number of second surgeries recommended as a result of final positive margins.
- j. Rate of second surgeries as a result of a positive margin status following SOC (control arm) and LUM Imaging procedures (device arm).
- k. Rate of cancer found in second surgeries
- l. Number of second surgeries for each patient
- m. Number of images per subject from the cavity after SOC and first round of therapeutic shaves
- n. Secondary analysis of sensitivity and specificity including imaging before removal of SOC shaves.
- o. Number of device issues and malfunctions and their impact to data capture.
- p. Patient-level sensitivity and specificity
- q. Collect exploratory data on tissue types found in therapeutic shaves.
- r. Collect exploratory data on patient reported outcomes.
- s. Analysis of tissue-level sensitivity and specificity for the SOC procedure based on the outermost SOC resected surface.
- t. Adverse events stratified by severity and relatedness to drug/device.
- u. Serious adverse events stratified by severity and relatedness to drug/device
- v. Adverse events by preferred term (sorted by descending occurrences for each preferred term).
- w. Summary of adverse events, overall and split by expectedness to drug/device.
- x. Comparison of adverse events in subjects that have at least one therapeutic shave versus subjects that have no therapeutic shaves.

4 Statistical methods

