4.1 Demographics and baseline characteristics

Demographic and baseline characteristic including: age, race and ethnicity, menopausal status, mammographic breast density, palpability, cancer histologic type, tumor size, node positive patients, and tumor receptor status (ER/PR/HER2), and baseline body mass index (BMI) calculated from weight and height will be summarized for the study sample. Statistics for continuous variables will include mean, median, standard deviation (SD), minimum, maximum and sample size for the overall sample and grouped by control and device arms, and two-sided 95% CI of the mean difference between (control and study arms). Binary variables will be described with frequencies and percentages for the overall sample. Demographic and baseline characteristics will be summarized by overall using descriptive statistics for analysis populations.

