4.5 Study sample size, event-driven design, and overall study power

The pivotal study is powered based upon targeting success for the three co-primary endpoints as outlined above. The efficacy endpoints will be assessed in the patients who undergo LUM-guided imaging (not the 1/10th of subjects randomized to the control arm).

Based on Phase C data, it is expected that 268 patients will provide the necessary 70 truth standard positive events to power for sensitivity. Also, based on Phase C data, it is expected that 152 patients will provide the necessary 1021 truth standard negative events to power for specificity. To power for the removal of residual cancer endpoint, approximately 220 patients are required. Thus, the size of this study is driven by the necessary number of truth standard positive events.

Adding 15% to the sample size of 268 patients to include subjects in the control arm and some expected data loss, it is estimated that 310 total patients will be needed for the pivotal study. However, given the uncertainty of translating the number of truth standard positive events to actual number of patients, the pivotal trial is planned as event-driven clinical study. Patients will be enrolled until 70 truth standard positive events are reported, up to a maximum of 450 patients. The number of truth standard positive events will be counted based on the truth standard hierarchical approach from Figure 2. Counting of these events will be conducted via software programming to read from the electronic data capture system; no endpoints will be calculated at that time. Results from the event counting process will be accessible to the DSMB which will then inform Lumicell

LUMICELL CONFIDENTIAL

This document is confidential. Do not disclose or use except as authorized.

personnel on whether the targeted number of events has been reached or if enrollment needs to continue.

With the proposed sample size from sensitivity, under the alternative hypothesis for specificity using the GEE model with a compound symmetry correlation structure, the power to show true specificity above the performance goal of > 60% will be >99%. For removal of residual cancer, the power is estimated at 96%. Thus, the overall study power is $90\% \times 99\% \times 96\% = 86\%$.

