4.7 Methods for additional analyses

Secondary outcomes involving proportions will be analyzed using methods for Binomial distributions akin to the ones described above. Continuous measurement will be summarized using means and standard deviation and 95% confidence intervals. The percent of people with a specific AE will be reported in prespecified groups. The percent of subjects with adverse events in subjects that have at least one therapeutic shave will be compared with the percent of subjects with adverse events that have no therapeutic shaves using Fisher's exact test or goodness of fit test.

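### Re-excision is listed by randomised arm, and reducing it against standard of care is a stated purpose, but no between-arm difference or interval is planned

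*SAP*

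**What the plan says.** **Purpose and design.** Protocol 3.2 says the system is meant to "eliminate or reduce the need for re-excision surgeries when compared with current standard of care procedures". Protocol 5.2.7 randomises 10:1 and reveals the allocation only after SOC surgery is finished. It gives mitigation of surgeon bias as the reason for randomising. Protocol section 1 describes the trial thus: "The objective of this prospective, multi-center, two-arm randomized, blinded study is to demonstrate the safety and efficacy". SAP section 1 says: "The objective of this prospective, multi-center, single-arm study is to demonstrate the safety and efficacy of the LUM Imaging System".

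**Re-excision.** SAP 3.3 endpoint j (Protocol 2.2 and 15.4.3, endpoint k) is "Rate of second surgeries as a result of a positive margin status following SOC (control arm) and LUM Imaging procedures (device arm". On method, SAP 4.7 says: "Secondary outcomes involving proportions will be analyzed using methods for Binomial distributions akin to the ones described above". The methods described above it are an exact binomial test and interval for one proportion (SAP 4.2), and binomial, GEE and bootstrap estimates of one sensitivity or specificity (SAP 4.3).

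**Reduction in re-excision.** SAP 3.3 endpoint b is the share of SOC-positive patients whose final margins are all negative after the Lumicell procedure. The SAP adds: "This endpoint also estimates the potential reduction in re-excision surgeries following standard of care breast-conserving surgery".

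**Who is analysed.** SAP 4.5 states: "The efficacy endpoints will be assessed in the patients who undergo LUM-guided imaging (not the 1/10th of subjects randomized to the control arm". SAP section 2 assigns secondary efficacy to the mITT set, defined by having been imaged. SAP 4.11.3 item c keeps every re-excised patient in the re-excision analysis but names no denominator.

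**Between-arm contrasts.** The one that is specified is for baseline variables (SAP 4.1): "two-sided 95% CI of the mean difference between (control and study arms".

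**The concern.** The purpose is comparative, a randomised control group exists, and the outcome is collected in both arms. Yet, followed as written, the plan yields two rates side by side and no estimate of how far they differ. One of them comes from a few dozen patients. Readers will subtract one from the other anyway, and the plan gives them no interval for the result.

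The figure that the plan does connect with fewer operations, endpoint b, is a before-and-after measure within the device arm. It follows patients who start with a positive margin and looks only for improvement. It does not answer whether patients assigned to the device had fewer operations than patients assigned to SOC alone.

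There is also a practical gap. If controls are outside the efficacy endpoints, endpoint j has no control rate to report. If they are inside, the denominator is not stated. Two analysts could build different tables.

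**Working it through.** **1. The plan's own figure.** SAP 4.5: 0.90 × 0.99 × 0.96 = 0.855, given as 86%. It reproduces. The factors are one-sample powers: sensitivity 60% against 40%, specificity 65% against 60%, residual cancer about 9% against 3%. No control-arm rate enters, so nothing below changes them.

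**2. Arm sizes.** At 10:1 the control arm is N/11.
- 406 enrolled (SAP 1.1): 406/11 = 36.9, so about 37 control and 369 device.
- 450 maximum: 450/11 = 40.9, so about 41 and 409.

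**3. What is contrasted between groups.**
- Baseline characteristics: by arm, interval for the mean difference (SAP 4.1).
- Adverse events: Fisher or goodness-of-fit test, by therapeutic shave taken or not, which is not the randomised comparison (SAP 4.7).
- Re-excision: a rate for each arm, with no difference, ratio, interval for either, or test.
- Margins, patient-reported outcomes and other efficacy outcomes: no between-arm contrast.

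**4. Are controls in the endpoint j set?** SAP 4.5 leaves them out of the efficacy endpoints, while endpoint j names them. Protocol 5.2.5 and 5.2.6 record cavity images before allocation is revealed, so controls could count as imaged and enter mITT. The footnote to Protocol Table 2 ties intraoperative imaging to the device arm, which would keep them out. Both readings are available.

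**5. What endpoint b measures.** In the device arm let *a* be the proportion with a positive margin after SOC, *c* the conversion rate among them (endpoint b), and *g* the proportion of all patients who are SOC-negative but have a positive outermost margin after a therapeutic shave. Final margin status rests on the outermost surface (Protocol 5.2.9).
- Final positive proportion: *a*(1 − *c*) + *g*
- Net relative reduction in positive margins: [*a* − *a*(1 − *c*) − *g*]/*a* = *c* − *g*/*a*

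Endpoint b reports *c* and so exceeds the net reduction by *g*/*a*. The documents give no value for *g*. As a scale only, each 1 percentage point of *g* takes off 1/17 = 5.9 points if *a* = 17%, and 1/59 = 1.7 points if *a* = 59% (the range of close or positive margin rates in Protocol 3.1). The step from margin status to the decision to re-operate is a further gap that *c* does not contain.

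**6. Precision of the missing contrast.** The documents assume no re-excision rate or effect for this trial. Assumptions here: control rate 10% to 33% (the upper end from the background figure of about a third in Protocol 3.1), and a halving in the device arm. Approximate 95% half-width = 1.96 × √[p₁(1 − p₁)/37 + p₂(1 − p₂)/369].

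For 20% and 10%: 1.96 × √(0.16/37 + 0.09/369) = 1.96 × √(0.004324 + 0.000244) = 1.96 × 0.0676 = 0.132. The control arm supplies 0.004324/0.004568 = 95% of that variance.

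| Control rate | Device rate | Half-width (points) | Fisher power, usual two-sided p | Fisher power, each tail ≤ 2.5% |
|---|---|---|---|---|
| 10% | 5% | 9.9 | 25% | 16% |
| 17% | 8.5% | 12.4 | 35% | 27% |
| 20% | 10% | 13.2 | 40% | 33% |
| 33% | 16.7% | 15.7 | 63% | 57% |

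The two power columns differ only in how the two-sided Fisher rule is defined. In the first three rows the half-width exceeds the assumed difference (5, 8.5 and 10 points), so an interval centred there would include zero.

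**7. What a confirmatory comparison would need.** For 80% power to detect a halving from 20% (two-sided 5%, normal approximation): about 98 controls and 98 × 11 = 1,078 patients at 10:1, or about 398 patients in total at 1:1.

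**The case against.** The strongest reply is that this design is deliberate and disclosed. Randomisation is there to stop the surgeon's SOC work being influenced by knowledge of the arm, the efficacy claims rest on performance goals, and both documents say that the control arm is not part of them. A group of about 37 was never offered as an efficacy comparator, so omitting a contrast that cannot be powered is defensible. That stands as an answer to any demand for a confirmatory test. It does not explain why an outcome listed by arm, and tied to a stated comparative purpose, should lack the one summary that compares the arms.

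A reader might infer more than the documents support:
- **That the rates would carry no uncertainty.** SAP 4.7 points to methods that include an exact two-sided 95% interval (SAP 4.2), so each rate would have its own. For example, 7/37 = 18.9% has an exact interval of 8.0% to 35.2%. Only the interval for the difference is missing.
- **That endpoint b claims every converted margin as an avoided operation.** The text speaks only of a potential reduction, and endpoints i to l count second surgeries recommended, performed and with cancer found.
- **That the clinical judgement on close DCIS margins in Protocol 3.1 undermines b.** Pure DCIS within 2 mm of ink is already positive under SAP 3.1, so those cases fall largely inside the definition.
- **That 86% is offered as two-arm power.** SAP 4.5 presents it as the product of the co-primary powers, directly after setting the control arm aside.
- **That the residual-cancer goal of 3% can serve as a control rate.** Controls have no therapeutic shaves, so that contrast is undefined. Nor is the 9/11 detection result in Protocol 3.2 a re-excision effect.

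Re-excision is also not the only stated aim observable in both arms: Protocol 3.2 names negative margins too. They are not contrasted either.

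**Conclusion.** The point holds as a gap in estimation, not as a fault in the primary analysis. The co-primary tests, their significance levels and the 86% stand. What is missing is a randomised estimate of the difference in re-excision, with its interval and a defined analysis set. Endpoint b cannot take its place, because it leaves out new positive margins and the decision to re-operate.

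With 37 against 369 patients, the 95% half-width would be about 10 to 16 points and the Fisher power 25% to 63% (usual two-sided p-value) or 16% to 57% (each tail at most 2.5%). These figures rest on assumed control rates of 10% to 33%, an assumed halving, and exact 10:1 allocation of 406 patients. They support reporting an estimate and rule out presenting the contrast as confirmatory.

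The two design labels, single-arm in SAP section 1 and two-arm randomised in Protocol section 1, conflict and should be reconciled.

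**What to change.** 1. In SAP 4.7, define the endpoint j analysis as the proportion of patients with at least one re-excision for a positive margin, device minus control, by assigned arm among all randomised patients. Report a risk difference with a two-sided 95% exact or score interval, labelled estimation only. State that this analysis includes the control arm despite the general exclusion in SAP 4.5, and give its denominator.
2. Present this interval beside endpoint b, and label b a within-arm conversion rate.
3. In SAP section 1, replace the single-arm label with a two-arm randomised trial whose co-primaries are tested against performance goals in the device arm.

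The cost is SAP wording and one table row, with no new patients, data or alpha. The drawback is a wide interval that may include no effect. The surgeon also knows the arm by the time re-excision is considered, so the contrast reflects surgical decisions as well as margins; the table should say so.
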